### Scientific Background

Low back pain is one of the most common musculoskeletal conditions requiring medical care and contributing to patient impairment and disability, with over 25% of the general population reporting low back pain at any given time and a lifetime incidence exceeding 80%. However, the care of low back pain represents one of the greatest challenges facing musculoskeletal care today. Current care for low back pain relies on a trial and error approach, with increasingly aggressive options considered after each failed treatment. This results in exposure of patients to unnecessary risks associated with treatments that are unlikely to be helpful, significant wasted resources, and delays in symptom improvement (1). In addition, disc degeneration is ubiquitous in our aging population (2-3), in whom standard treatments, including injections, surgery, and current medication options (particularly NSAIDs and opioids), carry increased risk. With increasing interest in the anti-aging effects of metformin, and potential effects in the intervertebral disc related to inflammation, anabolic activity and cell senescence (4), the favorable side effect profile and low cost make metformin an attractive therapeutic candidate for the treatment of low back pain. In addition, preliminary observational data in patients with low back pain taking metformin suggest an improvement in pain score compared to patients not taking metformin and over time (see below). With the suggested effects of metformin on the pain experience, inflammatory cascade (5), and microbiome (6), exploring the associations of these key biomarkers with response to oral metformin may reveal sub-populations of subjects more likely to respond to treatment as well as novel targets for future therapeutics. In addition, because degenerative changes and low back pain increase with age, and aging is associated with systemic inflammation, older adults may have an even greater response to a medication such as metformin, underscoring the potential opportunity of this treatment approach.

We have previously demonstrated associations of protein and genetic biomarkers with pain and function in axial low back pain (7-8). In addition, we queried the UPMC data warehouse to compare patients with low back pain who were taking metformin vs those taking other medications for their diabetes management. Diabetic patients taking metformin (n=26,077) had slightly lower average pain scores (6.2) than diabetic patients not taking metformin (n=21,540) (6.4). ESR was also lower for patients taking metformin (21.2 vs 26.4). Among patients not taking NSAID or oral steroid, average pain scores remained in favor of metformin (6.1 vs 6.4). We then queried the database to examine patient pain score one year after initial prescription of metformin (n=26,937) and demonstrated small improvement in average pain score, from 6.5 to 6.2 after one year of metformin. When these patients were limited to patients with an ESR of 10-30 (chosen based on above finding and prior evidence in low back pain (9-10), the average pain score improvement widened to 6.8 to 6.3. and was similar amongst patients without NSAID or steroid use (6.8 to 6.1). Finally, when subjects were further narrowed to patients with ESR 10-20, the pain score changed from 9 to 4, however, this resulted in extremely small sample size (n=2). These results justify to proposed prospective study (SA1), and also provide evidence of sub-phenotypes of patients who will be more likely to respond to treatment (SA2).

In addition to the above data, we have previously developed a clinical prediction model for patients with axial low back pain for response to epidural injection. While we accurately predicted 22% of the total population with this model, addition of protein and genetic polymorphism data into the predictive model as proposed herein improved the predictive capacity of the model, demonstrating the feasibility of this approach.

### Study Objectives

The purpose of the current study is to determine the effects of metformin in non-diabetic patients with low back pain, and identify novel targets for future treatments.

Specific Aim 1: To examine the response in pain and pain related function to oral metformin treatment for 6 months in patients with axial low back pain.

Hypothesis: Patients with axial low back pain treated with metformin for 6 months will demonstrate a 2 point or greater improvement in numeric pain rating score and be superior to placebo in pain and functional outcome measures.

Specific Aim 2: To examine the associations of clinical characteristics, genetic, protein and microbiome biologic signatures with response to treatment, and develop a robust personalized predictive model for determining response.

Hypothesis: Polymorphisms in pain perception genes, blood based protein biomarkers, and microbiome characteristics will show significant associations with response to metformin in regard to both pain and pain related function. In addition, older patients with moderate levels of systemic inflammation will demonstrate a greater response.

### Study Design & Methods

Randomized, placebo controlled, wait list controlled, clinical trial. Subjects will be randomized to one of the following groups:

-High Dose Metformin Group

-Low Dose Metformin Group

-High Dose Placebo Group

-Low Dose Placebo Group

-Wait-list Control Group (will have a 3 month "wait-list" and then be randomized to treatment group at month 3 visit)

Subjects will take study medication for a total of 6 months

## Eligibility Criteria

Inclusion criteria:

- Age 18 and above
- Diagnosed with axial low back pain (low back pain more severe than pain in other parts of the body, without radiation of pain into the lower extremities).
- Women of child bearing potential must have a negative serum pregnancy test at baseline.

Exclusion criteria:

- Diagnosed with rheumatoid arthritis, lupus, other autoimmune/systemic inflammatory arthropathies
- Progressive lower extremity weakness or numbness
- Recent oral or injected steroid use (within last 3 months)
- NSAID use
- Chronic kidney disease (eGFR <60)
- Diagnosis of diabetes mellitus or elevated HbA1c at screening (> 6.5)
- Subjects must not be pregnant or breastfeeding, or planning to become pregnant or breastfeed during the course of the trial
- Unable to take an oral medication in a non crushable pill form
- Taking metformin presently or within the last 6 months
- History of allergy to metformin
- History of lactic acidosis or elevated lactate at screening (> 2.2)
- Severe Hepatic dysfunction
- Currently taking a diabetic medication such as sitagliptin, saxagliptin, linagliptin, alogliptin, sitagliptin with metformin
- Currently taking a Carbonic anhydrase inhibitor such as topiramate, zonisamide, acetazolamide, dichlorphenamide, methazolamide
- Currently taking cimetidine

## Statistical Considerations

Sample size is estimated based on feasibility of subject recruitment based on prior study of axial low back pain, as well as prior studies demonstrating clinically and statistically significant change in the primary outcome of NPRS for randomized trials of NSAID in as few as 37-295 patients. For patients who met all inclusion criteria in our previous study

examining epidural steroid injection for axial low back pain, our successful recruitment rate was 72%. For this prior study, we screened 1455 subjects over a one year period, and 768 were excluded due to leg pain/radiculopathy. Therefore, we expect adequate availability of subjects to meet our recruitment goal. Formal sample size justification based on 80% power, alpha = 0.05:

Effect Sizes:

High vs. Low: 0.79

High vs. placebo: 0.79

Low vs. placebo: 0.79

Control vs. placebo: 0.86

\*These are all based on two-sample t-tests with a common variance.

Per MOD19010007-009: While we retained data from the initial enrollment, they not be included in the parent statistical analysis. Therefore, this would not impact the overall analysis plan since re-enrolled patients would complete the new proposed baseline data collection (ie treated as an entirely new subject).

Since there has been sufficient wash-out period for medication and the short time enrolled in the study, re-enrolling subjects is not expected to influence results

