Official Title: Effects of Metformin on Low Back Pain

ClinicalTrials.gov ID (NCT number): NCT04055012

Document Date: 12/11/2024

Statistical Analysis Plan

The primary outcome is change in pain score and disability score between baseline and 12 months, using the minimal clinically meaningful change. Sample size was estimated based on feasibility of subject recruitment based on prior study of axial low back pain, as well as prior studies demonstrating clinically and statistically significant change in the primary outcome of NPRS. However, given the early termination of the study prior to reaching an adequate sample size, outcome measures are reported with descriptive statistics only, ie. mean and standard deviation, with insufficient numbers to permit formal between group comparisons.

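### Does analysing re-enrolled patients as entirely new subjects, without a count or a wash-out length, undermine the reported means?

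*Protocol*

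**What the plan says.** The last paragraphs of the protocol's Statistical Considerations, attached to a numbered modification, deal with re-enrolment in three steps.

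- First-period data: "While we retained data from the initial enrollment, they not be included in the parent statistical analysis". A verb is missing, but the sense is clear: the data are kept but not analysed.
- Status on return: "re-enrolled patients would complete the new proposed baseline data collection (ie treated as an entirely new subject".
- Justification: "Since there has been sufficient wash-out period for medication and the short time enrolled in the study", followed by the conclusion that "re-enrolling subjects is not expected to influence results".

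The Eligibility Criteria exclude anyone "Taking metformin presently or within the last 6 months". The protocol does not say whether this criterion was applied again at re-entry.

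The SAP is a single paragraph. It states that "outcome measures are reported with descriptive statistics only, ie. mean and standard deviation", the reason being "given the early termination of the study prior to reaching an adequate sample size". It does not mention returning patients.

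**The concern.** The claim of no influence rests on two facts, wash-out and brevity of the first stay, and neither is given a length. Nor is the number of returners stated. Wash-out and a fresh baseline deal with drug carry-over and the starting value. They do not deal with who chose to come back, or with what a patient expects after an earlier spell in the same trial. The outcomes are pain and disability scores, for which expectation could plausibly matter.

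Because the trial stopped early, the means and standard deviations are the whole of the outcome reporting. No model or sensitivity analysis is planned in which returners could be examined. If they were numerous in a small arm and responded differently, its mean would describe a mixture that the reader could not take apart. An undisclosed wash-out length also leaves open whether re-entry agreed with the metformin-free interval in the Eligibility Criteria.

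**Working it through.** **1. What the plan already rules out.** Counting a patient twice would require both periods in the analysis set; the first is excluded. A contaminated change score would require the old baseline; a new one is collected. What remains is carry-over, selection and expectation.

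**2. Is there a contradiction on wash-out?** The Eligibility Criteria set a six-month metformin-free interval. Statistical Considerations give no figure. If returners are new subjects in the ordinary sense, the criterion applies again and supplies a minimum. That link is inferred, and the criterion covers metformin only. Without a stated wash-out length, the two sections cannot be shown to conflict.

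**3. Scale.** The documents give no figure on re-enrolment to reproduce and no planned arm size, so one has to be inferred. Statistical Considerations give an effect size of 0.79, 80% power, alpha 0.05 and a two-sample t-test. Assuming equal arms and a two-sided test:

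n = 2 × (1.960 + 0.842)² / 0.79² = 15.70 / 0.624 = 25.2, so 26 per arm by the normal approximation. The t-test gives 26.1, and the detectable effect at n = 26 is 0.792, which matches the stated 0.79. The other stated effect size, 0.86, gives 22.2, so 26 cannot be taken as the size of every arm.

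One returner whose change differs by δ moves an arm mean by δ/n. Take δ from 0 to 2 points (assumed; 2 is the improvement hypothesised in the Study Objectives: "will demonstrate a 2 point or greater improvement in numeric pain rating score"):

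- n = 26: 0 to 2/26 = 0.08 points
- n = 10 (assumed, for early termination): 0 to 2/10 = 0.20 points

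**4. Would means with and without returners settle it?** With k returners in an arm of n, differing by s standard deviations, the full mean differs from the mean without them by (k/n) × s. The chance variation of that difference, assuming equal SDs, is (k/n) × √(1/k + 1/(n − k)). Taking s = 0.79, the plan's own effect size, as a large assumed value:

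| n | k | Shift (SD units) | Chance variation (SD units) |
|---|---|---|---|
| 26 | 1 | 1/26 × 0.79 = 0.030 | 1/26 × √(1 + 1/25) = 0.039 |
| 10 | 1 | 1/10 × 0.79 = 0.079 | 1/10 × √(1 + 1/9) = 0.105 |
| 5 | 2 | 2/5 × 0.79 = 0.316 | 2/5 × √(1/2 + 1/3) = 0.365 |
| 10 | 5 | 5/10 × 0.79 = 0.395 | 5/10 × √(1/5 + 1/5) = 0.316 |

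In the first three rows the shift is smaller than its own chance variation. With half of an arm of 10 returning, it is 0.395/0.316 = 1.25 times that variation. The extra tables could not reliably tell a real difference from noise in any of these cases.

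**The case for a change.** The strongest reply is that the possible influence runs from negligible to material, and the number that would settle it is withheld. Two returners in an arm of five, differing by 0.79 SD, would shift the mean by 0.316 SD, which is 40% of the effect size the trial was designed to detect. First-period data were retained and the intervals were evidently known, so a count, a flag and a supplementary table would cost little. If returners were few, the disclosure would support the protocol's own statement.

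Part of this stands. The count, the first allocation and exposure, and the interval since last study drug belong in the participant flow of any report, and the text would be clearer if it said whether the entry criteria were re-applied. But these are facts to report. They do not alter who is analysed, from what baseline, or how. The 40% figure rests on an assumed arm size, an assumed number of returners and an assumed difference. Selection and expectation effects are possible, but nothing in the documents shows them. The modification may also hold the missing details, or may have been a restart of the whole study; the documents do not say.

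If returners were randomised afresh, as their treatment as new subjects suggests, nothing would steer them systematically to one arm.

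**Conclusion.** No change to the plan is needed. Re-enrolment is described briefly, but the analytic choices that matter are made: first-period data excluded, new baseline, one analysed record per patient. Following them is not shown to give a wrong or worse descriptive result. Type I error is not involved, because the SAP makes no between-group comparison, and no efficacy conclusion turns on the arm means.

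The true effect is unknown. On the assumptions shown, one returner moves an arm mean by at most 0.08 points at 26 per arm or 0.20 at 10 per arm, and by nothing if returners respond as new patients do. A larger effect needs several returners in a very small arm together with a large difference in response, and the documents give evidence of neither. Tables without returners would be an optional display with little power to inform.

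This conclusion assumes that treating returners as new subjects includes re-applying the entry criteria and randomising again. The documents suggest this but do not state it. The missing count and intervals are a minor reporting gap that analysts would ordinarily fill from the retained records.

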Official Title: Effects of Metformin on Low Back Pain

ClinicalTrials.gov ID (NCT number): NCT04055012

Document Date: 12/11/2024

Statistical Analysis Plan

The primary outcome is change in pain score and disability score between baseline and 12 months, using the minimal clinically meaningful change. Sample size was estimated based on feasibility of subject recruitment based on prior study of axial low back pain, as well as prior studies demonstrating clinically and statistically significant change in the primary outcome of NPRS. However, given the early termination of the study prior to reaching an adequate sample size, outcome measures are reported with descriptive statistics only, ie. mean and standard deviation, with insufficient numbers to permit formal between group comparisons.

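### The SAP's 12-month primary outcome falls after the 6-month treatment course, is not labelled off-treatment, leaves the wait-list baseline undefined, and does not directly address Aim 1

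*SAP*

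**What the plan says.** The SAP, a single paragraph, defines the primary outcome: "The primary outcome is change in pain score and disability score between baseline and 12 months, using the minimal clinically meaningful change". It adds that the trial stopped early and that outcome measures will be given as means and standard deviations, without formal comparison of groups. It attaches no time point to those summaries beyond the 12 months in the primary outcome.

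The protocol, under Study Design & Methods, states: "Subjects will take study medication for a total of 6 months". Wait-list patients wait 3 months "and then be randomized to treatment group at month 3 visit".

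Under Study Objectives, Specific Aim 1 reads: "To examine the response in pain and pain related function to oral metformin treatment for 6 months in patients with axial low back pain". Its hypothesis is that patients "treated with metformin for 6 months will demonstrate a 2 point or greater improvement in numeric pain rating score" and will do better than placebo on pain and function.

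Under Statistical Considerations the protocol identifies the primary outcome only in passing, when citing earlier studies that showed a "statistically significant change in the primary outcome of NPRS for randomized trials of NSAID". It gives no assessment time there. That section mentions fresh baseline data only for re-enrolled patients, not for wait-list patients when they start treatment.

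**The concern.** The aim concerns what happens over a 6-month course. The one primary summary that the SAP names is taken months after that course should have ended. Neither document states a durability or off-treatment objective, or gives a reason for 12 months.

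Two things are at stake:

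- A 12-month mean on its own cannot separate no response during treatment from a response that appeared and then faded. If it carries no label, a reader may take it as the answer to Aim 1.
- The SAP says baseline without defining it for patients who wait 3 months before treatment. Under one reading, the same mean pools patients at different distances from their last dose and from their first.

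Means and SDs are all that the trial will report, so the labels on them decide what can be concluded.

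**Working it through.** There is no stated figure to reproduce; the check is arithmetic on the timeline.

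**Inputs**
- Treatment duration: 6 months (protocol, Study Design & Methods).
- Wait before treatment: 0 months for direct entry, 3 months for the wait-list group (same section).
- Primary time point: 12 months from baseline (SAP).
- Assumptions: medication starts at randomisation to a treatment group, and the full 6 months is taken.

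**Formulas**
- Baseline at enrolment: months off medication = 12 − (wait + 6).
- Baseline at start of medication: months off medication = 12 − 6.

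**Results**
- Direct entry: 12 − (0 + 6) = 6 months off. This is 6/12 = 50% of the 12-month window.
- Wait-list, baseline at enrolment: treatment ends at 3 + 6 = 9 months, so 12 − 9 = 3 months off. The visit is 12 − 3 = 9 months after the start of medication, and the measured change includes the 3 months of waiting.
- Wait-list, baseline at start of medication: 12 − 6 = 6 months off, with the visit at 3 + 12 = 15 months after enrolment.
- Difference between the two entry routes at a visit 12 months after enrolment: 6 − 3 = 3 months off medication.

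Under either baseline, no patient following the planned schedule is on study medication at the primary time point.

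**Consequence for an end-of-treatment summary.** At a visit 6 months after enrolment, direct-entry patients have had 6 months of medication but wait-list patients only 6 − 3 = 3. For the wait-list group, the end of treatment is month 9 from enrolment. A 6-month summary therefore needs the same definition of baseline.

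**The case against.** The strongest reply is that the documents do not strictly contradict each other. In Aim 1, 6 months is the length of treatment, and no section states a 6-month primary assessment. Six months of treatment followed by a 12-month outcome is a coherent design, and a careful reader can work out from the protocol that patients are off medication by then. This stands in part: it rules out saying that the SAP breaks a stated assessment time. It does not supply a reason for 12 months or a persistence objective, and it does not make an off-treatment mean an answer to a question about response to treatment.

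Second, a reader might infer that Aim 1 will have no summary at all. The documents do not support that. The SAP refers to outcome measures in the plural without restricting their timing, so end-of-treatment results may yet be reported. What can be said is that none is specified.

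Third, the 3-month gap is conditional. It arises only for wait-list patients counted from enrolment. With a start-of-medication baseline, every patient is 6 months off and the mixing disappears. The documents also do not show how many wait-list patients, if any, reached month 12. This is correct, and it is why the baseline must be stated.

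Fourth, reporting is descriptive and numbers are small, so a 6-month mean could not establish a response either. That is true, and it limits the gain to correct labelling and a summary that matches the aim.

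**Conclusion.** The point holds as a matter of interpretation. Month 12 is 6 months after the last planned dose for direct-entry patients, and 3 or 6 months after it for wait-list patients, depending on a baseline that the SAP leaves undefined. The only named primary summary does not directly address Aim 1. With an enrolment baseline it would also pool patients 3 and 6 months off study medication. No test, error rate or power figure is affected. The figures assume that medication starts at randomisation and that the full course is taken.

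Two stronger readings should be avoided:

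- A reader might infer that one of the two time points is post hoc. The 12-month outcome appears only in the SAP, which was written with early termination known, while 6 months of treatment is in the protocol's aim. Neither fact establishes when either assessment time was chosen.
- A reader might infer that any effect would have gone by month 12. The documents give no information on pain or function after metformin is stopped.

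**What to change.** Reconcile the SAP with the protocol's Study Objectives and Study Design & Methods sections on assessment time and baseline.

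1. Keep the 12-month outcome. Label it off-treatment and give the months since the last planned dose.
2. Beside it, report the mean and SD of the change in NPRS and disability score from the start of study medication to the end of the 6-month treatment period, identified as the summary that addresses Aim 1.
3. State in the SAP which baseline applies to wait-list patients. Counting from the start of medication puts all patients on one clock. Report any wait-list visit made 12 months after enrolment separately, as 9 months from start and 3 months off medication.
4. For both time points, state neutrally when each was specified relative to termination.
5. If end-of-treatment data were not collected, say that Aim 1 has no matching summary, and do not present the 12-month change as the response to 6 months of metformin.

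The cost is some wording and one more set of means and SDs, or a sentence of limitation if the data do not exist. The documents show no visit schedule, so the sponsor must confirm which applies. The downside is that the added summary may be post hoc, and reporting both time points would not undo that. No change to dosing is proposed.

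### After early termination the SAP limits reporting to mean and SD, which leaves the randomised metformin-placebo contrast without an estimate or an interval

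*SAP*

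**What the plan says.** The SAP is a single paragraph. It names change in pain score and disability score from baseline to 12 months as the primary outcome. Then, "given the early termination of the study prior to reaching an adequate sample size", it says that "outcome measures are reported with descriptive statistics only, ie. mean and standard deviation, with insufficient numbers to permit formal between group comparisons". It plans no between-group difference and no confidence interval, and it does not mention n per group.

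The protocol sets a comparative question. Under Study Objectives, the Specific Aim 1 hypothesis is that treated patients "will demonstrate a 2 point or greater improvement in numeric pain rating score and be superior to placebo in pain and functional outcome measures". Study Design & Methods lists five randomised groups: high-dose and low-dose metformin, a "High Dose Placebo Group", its low-dose counterpart, and a wait-list group that is randomised to treatment at month 3. Statistical Considerations gives effect sizes for two-sample t-tests, including "High vs. placebo: 0.79" and "Low vs. placebo: 0.79", with one placebo comparator. It contains no analysis model, table layout or plan for intervals, so it does not fill the gap.

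**The concern.** A randomised placebo group is there to supply a comparison. Change from baseline within the metformin groups also contains placebo response and regression to the mean, and only the contrast with placebo removes these. Separate means and SDs leave readers to form that contrast themselves, and they show its uncertainty only to a reader who works it out.

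Dropping a test and dropping an estimate are different decisions. Low power makes a non-significant p-value uninformative. An interval from the same data shows directly how much, or how little, the trial says about metformin against placebo. A terminated trial can still contribute that, for instance to a later synthesis. The SAP's reason covers the test only.

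**Working it through.** **1. What the plan's figures imply.** Inputs from Statistical Considerations: 80% power, alpha 0.05, two-sample t-test with common variance, effect 0.79. I assume that the test is two-sided, that the effect is in SD units and that groups are equal; the documents state none of these.

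- Normal approximation: n = 2 × (1.960 + 0.842)² / 0.79² = 15.70 / 0.624 = 25.2, so 26 per group.
- Exact t-test: 26.1 per group. The detectable effect is 0.792 at 26 per group and 0.777 at 27.

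The stated 0.79 therefore corresponds to about 26 per group. "High vs. Low: 0.79" equals the two metformin-placebo figures, which fits one placebo comparator of about the size of a single metformin group. That supports pooling the two placebo groups. The allocation ratio is not stated, so an unequal case is shown below.

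**2. Is dropping the tests justified?** Exact t-test power for an effect of 0.79 is 20% at 5 per group, 39% at 10, 55% at 15 and 68% at 20. The SAP says that adequate size was not reached, so omitting tests is reasonable.

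**3. What an interval would show.** Half-width of the 95% CI for a difference in mean change:

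t(0.975, n1 + n2 − 2) × SD × √(1/n1 + 1/n2)

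Neither the achieved n nor an SD is in the documents. I assume an SD of change in pain score of 1.5 to 3.0 points and take group sizes from 2 up to the implied 26. No disability scale is named, so only pain is quantified.

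| Group sizes | Half-width, SD units | SD 1.5 (points) | SD 3.0 (points) |
|---|---|---|---|
| 2 v 2 | 4.30 | 6.45 | 12.91 |
| 5 v 5 | 1.46 | 2.19 | 4.38 |
| 10 v 10 | 0.94 | 1.41 | 2.82 |
| 20 v 20 | 0.64 | 0.96 | 1.92 |
| 26 v 26 | 0.56 | 0.84 | 1.67 |
| 5 v 10 | 1.18 | 1.77 | 3.55 |

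Example, 5 v 5: 2.306 × √(2/5) = 2.306 × 0.632 = 1.46 SD; × 1.5 = 2.19 and × 3.0 = 4.38. The last row is a pooled placebo group twice the size of a metformin group: 2.160 × √(1/5 + 1/10) = 2.160 × 0.548 = 1.18 SD.

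An interval can be computed at every size from 2 per group. At 5 per group its half-width (1.46 SD) is nearly twice the effect for which the trial was sized (0.79 SD); at 20 per group (0.64 SD) it is smaller than that effect.

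**The case against.** Descriptive reporting of a terminated trial is a defensible choice. The SAP states the termination openly, gives its reason and claims no efficacy. By-group mean, SD and n would let any reader derive the unadjusted difference and its interval. If enrolment was very small, the interval would add little to what the SAP already says in words. All of this stands, and it keeps the point at low severity. It does not remove it: the stated rule plans no contrast, and a wide interval puts a size on the uncertainty.

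Three stronger readings are tempting and are not supported.

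- *That groups will be merged or n withheld.* The SAP does not promise results by group with n, but its reference to comparisons between groups implies that groups are distinguished. This is missing detail, not a plan to hide anything.
- *That mean and SD cannot report the primary outcome because it is a responder outcome.* The phrase "using the minimal clinically meaningful change" might suggest this, but the SAP does not say so and sets no threshold.
- *That intervals should be judged against 2 points.* The 2-point figure in Specific Aim 1 is improvement in metformin-treated patients. The documents do not make it a margin between groups.

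**Conclusion.** The point holds as a low-severity reporting improvement. Small numbers justify omitting significance tests, but they do not justify leaving the contrast of Specific Aim 1 without an estimate and its uncertainty. Nothing in the plan's arithmetic is wrong, and no conclusion of efficacy is at risk, because none is claimed.

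How informative the added interval would be cannot be settled from the documents. Over the assumed range (2 to 26 per group in equal groups, SD 1.5 to 3.0 points) the half-width runs from 0.8 to 12.9 points. The documents do not support a group-size cut-off for showing the difference or a rule for baseline adjustment, and none is proposed here.

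**What to change.** Replace the restriction to mean and SD with the following:

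- n, mean and SD of change in pain score and in disability score, by randomised group.
- The high-dose minus placebo and low-dose minus placebo differences in those changes, with 95% CIs. Label them exploratory, make no significance claim, and pool the two placebo groups, as the single placebo comparator in the protocol's Statistical Considerations implies.
- The time point to which these results refer. The SAP's 12 months and the protocol's 6 months of treatment must be reconciled first.
- How wait-list patients randomised to treatment at month 3 are counted, since they belong to the wait-list group first and to a treatment group afterwards.

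The cost is a short paragraph in the SAP and one table from data already collected. There are two downsides. The intervals may be very wide. A reader may also treat a 95% CI as a test, which is why the exploratory label matters, particularly in a SAP written with the termination already known.
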